In this project, we hypothesize that aberrant epileptiform and seizure activity occurs in the hippocampus in patients with AD, and that suppression of epileptiform activity will improve memory deficits. We will study hippocampal activity using a proxy for epileptiform activity, Arterial Spin Labeling MRI (ASL-MRI), as well as EEG. We have completed a study of brain perfusion in mild-AD using Arterial Spin Labeling MRI (ASL-MRI), a non- invasive technique to quantifiably measure cerebral blood flow²³. We found decreases in cerebral perfusion in lateral temporal and parietal cortex, in agreement with previous PET studies. In addition, we found increased perfusion in the hippocampus, particularly when the perfusion measure was corrected for atrophy²³, Figure 2. These unexpected findings were recently corroborated^{24, 25}. A similar pattern of increased hippocampal activity has been seen with functional MRI, where patients with mild cognitive impairment show increased activation, a finding recently extended to presymptomatic patients with familial AD^{26, 27}. Hippocampal hyperperfusion can also be seen in

mild cognitive impairment and even in healthy elderly patients with apoE4 allele, which predisposes to development of AD.

[figure not shown]

Figure 2. Arterial spin labeling is a non-invasive technique to measure cerebral perfusion by applying a magnetic “tag” to arterial blood without requiring administration of a contrast agent (panel A). We have previously found increased hippocampal perfusion in AD participants that was visible at the individual level (top of panel B is AD participant, bottom is age-matched control). The perfusion change was prominent at the group level (panel C shows individual data points, panel D shows statistical maps of group data and panel E shows areas of both decreased perfusion in temporal-parietal cortex (in red) and increased perfusion in medial temporal structures (in green).

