In our previous study of 22 AD participants (mean age=75.6, MMSE 22.2) and 16 demographically matched controls (mean age=72.6, MMSE 27.9), we measured hippocampal, amygdala, and parahippocampus CBF as a % of visual cortex. In addition, we corrected for atrophy on a voxel-by-voxel basis by measuring gray matter volume in each voxel using T1 maps that were acquired in the same sequence as the perfusion maps. A region of interest analysis was performed using an *a priori* template, with left and right regions averaged together. The table below shows the results of the atrophy-corrected perfusion measurements as a percentage of visual cortex perfusion.

	Hippocampus	Amygdala	Parahippocampus
Mean AD (SD)	0.96 (0.29)	0.61 (0.19)	0.74 (0.20)

Mean CN (SD)	0.77 (0.17)	0.52 (0.11)	0.62 (0.14)
Prob of difference	0.008	0.043	0.017

Choice of levetiracetam as a pharmacologic probe

In this pilot study, we aim to determine whether the hippocampal hyperperfusion seen on ASL-MRI reflects abnormal epileptiform activity by using levetiracetam as a pharmacological probe. Even intermittent epileptic discharges, in the absence of clinically obvious seizures, may lead to memory impairment. If so, a reduction of hippocampal epileptiform activity could improve declarative memory and potentially alter progression of AD.

Levetiracetam, a newer antiepileptic drug, decreases the frequency and limits propagation of epileptiform activity without affecting normal neuronal excitability^{28, 29}. The mechanism of action of levetiracetam is not fully understood, but it binds specifically to synaptic vesicle protein SV2A and likely modulates its function³⁰. Levetiracetam may also have an indirect effect on GABA-A inhibitory neurotransmission and on high-voltage activated calcium channels. Levetiracetam decreases cortical excitability measured by transcranial magnetic stimulation³¹. In a study of levetiracetam in photosensitive epilepsy, 250mg oral doses decreased epileptiform activity induced by photic stimulation within 1 hour, and 750mg oral doses completely abolished epileptiform activity³². Acute dosing of levetiracetam 500mg caused significant reduction in the frequency of interictal epileptiform activity in 8/10 patients with epilepsy³³. Because of its rapid onset of action and effect on interictal epileptiform activity as well as seizures, levetiracetam is an excellent candidate AED to examine changes in perfusion on ASL-MRI.

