Twenty subjects with mild AD (MMSE≥20) will participate in this study in the Clinical Research Center at Beth Israel Deaconess Medical Center. Subjects will be screened to ensure they meet inclusion and exclusion criteria and will provide written informed consent before any study procedures are performed. Each eligible subject will undergo three sessions, held 1-2 weeks apart, in a double blind, within-subject crossover design, counterbalanced for order (placebo / levetiracetam 2.5 mg/kg / levetiracetam 7.5 mg/kg), Figure 3. During each session, placebo or levetiracetam will be administered intravenously over 20 minutes. Drug administration will occur during EEG recording so that neurophysiological recordings can be acquired before, during, and after administration. Changes in EEG background frequency and level of synchrony will be analyzed⁴⁴⁻⁴⁶. After drug administration and EEG recording, hippocampal perfusion and functional connectivity will be measured with ASL-MRI and resting BOLD fMRI. Finally, participants will undergo a cognitive battery with memory tests particularly sensitive to hippocampal function (declarative memory, attention, working memory and executive function).

[figure not shown]

Figure 3. Overall paradigm. Participants will undergo testing in 3 sessions counterbalanced for order, with placebo, low dose LEV or higher dose LEV. Drug will be administered intravenously during EEG recording. Imaging will be acquired with anatomical, perfusion and resting state bold MRI. Cognitive testing will be performed with a battery including a memory test particularly sensitive to hippocampal function as well as other tests of frontal function.

2. Study Rationale

This protocol has three primary goals: to test the hypothesis that increased hippocampal perfusion in AD is at least partially driven by epileptic activity, that lowering epileptic activity may improve cognitive performance, and that perfusion MRI can be used as a non-invasive assay of the effects of medications that decrease epileptic activity in AD.

3. Subject Recruitment and Screening

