For each session, the BIDMC research pharmacy will prepare study drug (intravenous levetiracetam 2.5mg/kg, levetiracetam 7.5mg/kg, or identical-appearing placebo) according to the subject's assigned group. Commercially-available levetiracetam will be purchased using study funds. All IV study drug will be prepared, labeled, and dispensed by the research pharmacy in accordance with clinical GMP guidelines. All study drug will be stored in a secure location. The study drug will be administered over 20 minutes by a research nurse in the BIDMC General Clinical Research Center. Study drug will be infused at room temperature.

n. Imaging paradigm

All participants will undergo brain imaging with a structural MRI, a resting brain perfusion MRI using arterial spin labeling, and a resting BOLD fMRI for functional connectivity. Imaging will be acquired on a 3.0T research-dedicated General Electric scanner.

1. Structural MRI - A high-resolution MPRAGE sequence will be performed with 1x1x1mm isotropic voxels to allow for accurate measures of atrophy. This sequence requires 7 minutes for acquisition.

2. Perfusion MRI - Arterial spin labeling perfusion MRI will be performed using a custom sequence that employs several features to increase reliability for clinical studies: background suppression to reduce motion related noise and artifacts; fast spin echo imaging to eliminate distortion and susceptibility related signal attenuation; and a long post-labeling delay to insure labeled blood actually reaches brain tissue of interest (Dai et al., 2008). For quantification of the blood flow corrected for atrophy, a second, anatomical imaging acquisition with the identical imaging sequence as the perfusion sequence will be performed but with two inversion preparations replacing the ASL. We have successfully employed this sequence and method of atrophy correction in patients with Alzheimer's disease (Alsop et al., 2008). This sequence requires 10-15 minutes for acquisition.

3. Functional Connectivity MRI- A resting BOLD fMRI sequence will be applied a rapid-acquisition echoplanar sequence (TE 25msec, TR 2500ms, 3.75mm isotropic voxels) over a 10 minute epoch to measure correlated activity at low frequencies, a measure of the strength of functional connectivity.

o. Behavioral testing

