We will do two analyses, one focused specifically on hippocampal perfusion and a second analyzing regional CBF throughout the whole brain. First, we will use a repeated measures ANOVA with hippocampal perfusion and session (placebo, 2.5mg/kg and 7.5mg/kg) being the factors. Hippocampal perfusion is measured as a percentage of visual cortex perfusion, using a template available within the Statistical Parametric Mapping package. Second, we will measure regional CBF throughout the whole brain using SPM5 and measure changes after drug vs. placebo using a random effects model and accounting for the repeated measures design. In addition to direct analysis of perfusion, we will examine cortical changes in CBF correlated with our seed region in the hippocampus. We predict that decreases in perfusion in the hippocampus after levetiracetam will correlate with increases in perfusion in association cortical regions. Lastly, we will test for correlations between behavioral measures of memory and regional changes in CBF in hippocampus and whole brain. We predict that decreases in hippocampal perfusion will paradoxically correlate with improved declarative memory performance.

EEG Data

EEG will be visually analyzed for presence of epileptiform activity. Peak alpha power, beta band power, delta/theta power, and coherence will be calculated using BESA (Brain Electrical Source Imaging) software and Persyst MagicMarker software. Measures will be analyzed using repeated measures ANOVA. We hypothesize that levetiracetam will decrease source coherence in temporal regions.

Analyses will be performed in the Cognitive Neurology Unit, Magnetic Resonance Imaging Center of the Department of Radiology, and EEG Laboratory at Beth Israel Deaconess Medical Center.

C. Subject Selection

Subjects will be recruited from the Cognitive Neurology Unit at BIDMC. The P.I., who specializes in neurodegenerative disorders, maintains an active clinic and treats over 100 patients with AD. In addition, the Cognitive Neurology Unit has over 13,000 patient visits per year.

Inclusion Criteria:

- Meets the NINCDS-ADRDA criteria for probable Alzheimer's disease
- Mild AD (MMSE \geq 20)
- Age \geq 50 years
- English as first language

Exclusion Criteria:

- A history of seizures prior to the onset of AD
- Familial Alzheimer's Disease due to known genetic mutations
- Current use of an anti-epileptic medication

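### The primary hippocampal outcome is a ratio to visual cortex perfusion, and nothing tied to the primary result checks that levetiracetam leaves that reference region in step with the rest of the brain

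*Combined protocol and SAP*

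**What the plan says.** The first planned imaging analysis (B3.B, Data Analysis, Imaging Data) is a repeated measures ANOVA across placebo, 2.5 mg/kg and 7.5 mg/kg. Its scale is fixed there: "Hippocampal perfusion is measured as a percentage of visual cortex perfusion". The scale is inherited from the group's earlier comparison of 22 AD participants with 16 controls, reported in B2: "we measured hippocampal, amygdala, and parahippocampus CBF as a % of visual cortex".

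B2 gives no visual cortex perfusion on levetiracetam. Its indirect evidence points both ways. Under the choice of levetiracetam as a probe it reports "Levetiracetam decreases cortical excitability measured by transcranial magnetic stimulation", and, in photosensitive epilepsy, "250mg oral doses decreased epileptiform activity induced by photic stimulation within 1 hour". The same subsection says that the drug "limits propagation of epileptiform activity without affecting normal neuronal excitability".

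On timing, the Study Overview (B3.A.1) says: "After drug administration and EEG recording, hippocampal perfusion and functional connectivity will be measured with ASL-MRI". The visit list in B3.A.6.b has the same order. EEG is recorded before, during and after the infusion, but no ASL scan before dosing is listed.

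Absolute flow should be obtainable. B2 calls ASL a "technique to quantifiably measure cerebral blood flow", and the imaging paradigm (B3.A.5.n) plans a second acquisition "For quantification of the blood flow corrected for atrophy".

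A secondary whole-brain analysis compares regional CBF on drug and placebo. The plan does not say whether that CBF is absolute or normalised. Nor does it say so for the Aim 2 correlations between the hippocampal seed and cortex.

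**The concern.** In a patient-control study the ratio is a sensible way to remove differences in overall flow. Within one person on drug and on placebo, the denominator is itself exposed to the drug. A fall in the ratio may then come from a lower numerator or a higher denominator, and the ratio alone cannot say which.

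The assumption needed is narrower than an unchanged visual cortex. If the drug moves flow by the same proportion everywhere, the ratio is unaffected. What matters is a visual cortex change out of proportion to the rest of the brain. The crossover does not remove such a change, because it would be present in the drug sessions and absent in the placebo session.

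Aim 1 makes a causal claim about the hippocampus. A disproportionate visual cortex rise could be read as support for it, and a disproportionate fall could hide a real effect. The whole-brain analysis includes visual cortex, but it is secondary, its scaling is unstated, and it is given no role in qualifying the primary result.

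**Working it through.** **Inputs.** From the B2 table: AD hippocampal ratio 0.96 (SD 0.29), control 0.77 (SD 0.17), so the planned drop is 0.96 - 0.77 = 0.19. From the Sample Size Justification: n = 20, power 72%, full return to the control level. Not given, so assumed: two-sided 0.05, within-subject correlation rho of 0.5 to 0.8, and every visual cortex shift v.

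**1. The plan's own figure.** Two independent groups of 20, normal approximation:
- SD = sqrt((0.29² + 0.17²)/2) = 0.238
- SE = 0.238 × sqrt(2/20) = 0.0752
- z = 0.19/0.0752 = 2.53; power = Φ(2.53 - 1.96) = 71.5%

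This matches 72%, although other methods come close too. It is computed on the ratio scale, so it takes v as zero.

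**2. Effect of a denominator shift.** Observed ratio on drug = (ratio with a stable denominator)/(1 + v). The illustration is a paired t-test (noncentral t, 19 df) with SD of the difference = 0.29 × sqrt(2(1 - rho)), which is 0.290 at rho 0.5 and 0.183 at rho 0.8. SDs are not rescaled by 1/(1 + v).

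| Disproportionate visual cortex shift | True hippocampal state | Apparent drop | Chance of a significant fall |
|---|---|---|---|
| none | falls to 0.77 | 0.190 | 79-99% |
| -2% | falls to 0.77 | 0.96 - 0.77/0.98 = 0.174 | 72-98% |
| -5% | falls to 0.77 | 0.96 - 0.77/0.95 = 0.149 | 59-93% |
| -10% | falls to 0.77 | 0.96 - 0.77/0.90 = 0.104 | 33-68% |
| none | unchanged | 0 | 2.5% |
| +2% | unchanged | 0.96 - 0.96/1.02 = 0.019 (10% of 0.19) | 5-6% |
| +5% | unchanged | 0.96 - 0.96/1.05 = 0.046 (24%) | 10-18% |
| +10% | unchanged | 0.96 - 0.96/1.10 = 0.087 (46%) | 25-52% |

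A rise of 0.96/0.77 - 1 = 24.7% would produce the whole planned drop. A fall of 1 - 0.77/0.96 = 19.8% would cancel it.

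**3. Which measures separate the explanations.** Values are drug/placebo multiples. The full hippocampal effect is 0.77/0.96 = 0.80, and the reference is taken to move only with global flow.

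| Scenario | Hippocampus/visual | Hippocampus, absolute | Visual, absolute | Hippocampus/reference | Visual/reference |
|---|---|---|---|---|---|
| Hippocampal fall only | 0.80 | 0.80 | 1.00 | 0.80 | 1.00 |
| Visual cortex +10% only | 0.91 | 1.00 | 1.10 | 1.00 | 1.10 |
| Visual cortex +10% relative, global -10% | 0.91 | 0.90 | 0.99 | 1.00 | 1.10 |
| Hippocampal fall, global +10% | 0.80 | 0.88 | 1.10 | 0.80 | 1.00 |

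In the third row the ratio and absolute hippocampal CBF both fall and absolute visual cortex CBF barely moves, yet the hippocampus has fallen no more than the rest of the brain. Only the second reference shows this.

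Simulation agrees (n = 20; SD of log-ratio change 0.19 to 0.30 split equally between regions; global-flow SD 0 to 0.2; all assumed). Given a significant ratio fall in the third scenario, mean absolute hippocampal CBF also falls in 99-100% of trials, and its 95% interval lies below zero in 57-99%. In the fourth, a true full effect keeps that interval below zero in only 49-98%.

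**4. Aim 2 scaling.** Illustrative log changes with no true link: hippocampus = g + e1, visual = g + k + e2, cortex = g + k + e3, with unit variances except var(k) = 0.25, 1 or 2.25.
- Visual cortex ratio against absolute cortical CBF: r = -var(k)/(2 + var(k)) = -0.11, -0.33, -0.53. By Fisher z at n = 20, a false result of the predicted sign occurs in 7%, 30% or 68% of trials.
- Both absolute, or both as visual cortex ratios: r = 1/sqrt(2(2 + var(k))) = +0.47, +0.41, +0.34, away from the predicted sign.

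**The case against.** **No denominator effect is shown.** The photic result concerns provoked discharges in photosensitive epilepsy, not resting flow in AD, and B2 also says that normal excitability is spared. This stands. A reader might infer that levetiracetam does alter visual cortex perfusion and that the primary result is therefore biased; the documents give no such evidence.

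**The ratio has a good purpose.** It cancels global flow changes, which absolute CBF does not. This stands too, and is why the ratio should remain primary.

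**The whole-brain analysis already covers visual cortex.** Partly true. It might reveal a large shift, but with unstated scaling and no link to the primary conclusion it is not a planned check.

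**The power illustration is not the plan's test.** Correct. The plan quotes 72% and uses a three-session ANOVA; the 79-99% baseline is a paired comparison with SD 0.29 in both states. With SD 0.17 on drug, the SD of the difference is sqrt(0.29² + 0.17² - 2 × rho × 0.29 × 0.17) = 0.252 or 0.185. Power is then 89-99%, falling to 42-67% with a 10% visual cortex fall. The pattern is the same.

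**Aim 2.** A reader might infer that the predicted correlation is built in. That needs the visual cortex ratio to be paired with absolute cortical CBF, which no section plans, and the variances are invented. What remains is that the scale is unstated.

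**Conclusion.** The concern holds as an unprotected assumption. The primary ratio supports a hippocampal conclusion only if visual cortex perfusion keeps step with the rest of the brain on levetiracetam, and nothing tied to the primary result would show whether it does. With assumed disproportionate shifts, 2% is minor, 5% is noticeable, and 10% either supplies nearly half of the planned drop or removes nearly half of it. These sizes rest on the B2 means and SD, the assumed correlation of 0.5 to 0.8, and shifts for which the documents give no value.

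Two stronger conclusions a reader might draw are not supported. The 72% figure is not shown to be wrong; it is conditional on a stable denominator. And a fall in absolute hippocampal CBF would not by itself settle the matter, because a global drug effect can produce it.

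Confidence is medium. The change is worth making before unblinding, since it affects what Aim 1 can claim and costs little.

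**What to change.** 1. Keep the visual cortex ratio as the primary imaging outcome.
2. Prespecify, as supportive analyses, the same repeated measures ANOVA on (i) absolute atrophy-corrected hippocampal CBF, (ii) visual cortex CBF, and (iii) hippocampal and visual cortex CBF, each relative to a second reference such as global grey matter CBF. Report all by session with confidence intervals.
3. State that, if these analyses do not support a hippocampal change, the Aim 1 conclusion will be limited to a change relative to visual cortex. Do not adopt a rule that labels a ratio change hippocampal because absolute hippocampal CBF moved the same way.
4. State the scaling of the whole-brain analysis. For Aim 2, put the hippocampal seed and the cortical values on the same stated scale, and do not correlate the visual cortex ratio with absolute cortical CBF. Note that a common scale is not bias-free: shared global flow or a shared denominator pulls the correlation away from the predicted sign.

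**Cost.** A little more analysis, with no new scans or participants. Absolute CBF is noisier and carries global flow changes, and the second reference brings a stability assumption of its own, so these analyses stay supportive. At n = 20 the 95% interval half-width is 2.093/sqrt(20) = 0.47 SD of the within-person change (about 0.09 or 0.14 log units if that SD is 0.2 or 0.3, assumed). A non-significant visual cortex change would therefore not prove stability.

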PART B STUDY DESCRIPTION

TITLE OF PROTOCOL	Seizure-like Hippocampal Activity in Alzheimer's Disease Neurodegeneration		
Principal Investigator	[name].		
Co-Investigators	[name]; [name]; [name]		
Mailing Address	[name]		
E-Mail Address	[contact]		
P.I.'s Telephone	[name]	P.I.'s Pager [name]	Fax: [name]
Sponsor/Funding Source	Fidelity Biosciences Research Initiative; Neurology Department internal funding		

B1. PURPOSE OF PROTOCOL

To test the hypothesis that increased hippocampal perfusion on arterial spin labeling MRI in patients with Alzheimer's Disease (AD) is partially driven by focal epileptiform activity, and that this abnormal activity contributes to memory dysfunction.

Here we propose applying an imaging technique, arterial spin labeling MRI (ASL-MRI), ideally suited for testing this hypothesis. We will utilize a pharmacological probe, levetiracetam, to test whether sub-clinical epileptiform activity is driving increases in hippocampal perfusion and contributing to the declarative memory impairment in AD. Levetiracetam is an antiepileptic drug (AED) that inhibits epileptiform activity. Levetiracetam inhibits burst firing without affecting normal neuronal excitability. We will study patients with mild AD in three sessions, counterbalanced for order, in a crossover design. In each session, participants will undergo a baseline electroencephalogram (EEG). They will then be given either a placebo or intravenous levetiracetam low dose (2.5 mg/kg) or high dose (7.5 mg/kg). After drug administration, repeat EEG, ASL-MRI perfusion imaging, and behavioral testing will be conducted. Participants will return at 1-2 week intervals for the second and third sessions in the other conditions (levetiracetam low dose / levetiracetam high dose / placebo). This study will test whether increased hippocampal perfusion in AD is caused by epileptiform activity, whether this activity is contributing to memory impairment, and whether antiepileptic medications might be a new avenue of treatment in AD. If validated, ASL-MRI would be an ideal tool to non-invasively determine whether antiepileptic medications are effective in decreasing aberrant excitatory activity in the hippocampus in AD.

Aim 1: To determine whether increased hippocampal perfusion in AD is caused by epileptiform activity.

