Hypothesis 1: Hippocampal perfusion in AD will be decreased after the administration of an antiepileptic medication, levetiracetam, but not after placebo.

Aim 2: To determine whether inhibition of burst firing can improve cognitive performance and neural function in cortical regions beyond the hippocampus.

Hypothesis 1: Decreases in hippocampal perfusion will correlate with improvements in

measures of declarative memory and spatial memory.

Hypothesis 2: Decreases in hippocampal perfusion will correlate with increases in cortical perfusion, particularly in lateral temporal and parietal association cortices.

B2. SIGNIFICANCE AND BACKGROUND FOR THE STUDY

Seizures and Alzheimer's Disease

Alzheimer's disease (AD) is associated with an increased risk of unprovoked seizures and accounts for approximately 2% of all epilepsy¹. Clinical seizures develop in 1.5 -17% of long-term AD survivors, most commonly in those with early age at disease onset and with familial AD²⁻⁴. In familial AD due to mutations in presenilin, epilepsy is much more prevalent, approaching 80% of affected members⁵⁻⁷. Seizures may be more common in sporadic AD, however, than previously reported⁸. Seizures may be under-recognized in patients with dementia. Subjective seizure auras such as *déjà vu*, olfactory hallucinations, and other auras are uncommon in AD³. Clinical manifestations of temporal lobe seizures are often subtle. For example, focal seizures restricted to the hippocampus may produce only mild confusion or amnesia without other outward signs⁹. Fluctuations in memory or wandering in AD can be due to unrecognized complex partial seizures¹⁰. Such seizures might easily be missed in patients with baseline memory and cognitive deficits. Seizures in AD are usually considered to be rare and late byproducts of a diffuse neurodegenerative process, but recent evidence from animal studies has raised the intriguing possibility that epilepsy plays a more central role in the pathophysiology of AD.

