We plan on testing twenty AD participants (> age 50 years) meeting the NINCDS-ADRDA criteria for probable AD from the Cognitive Neurology Unit at BIDMC. All participants will have mild AD by the Mini-Mental Status Examination (MMSE \geq 20). The P.I., who specializes in neurodegenerative disorders, maintains an active clinic and treats over 100 patients with AD. In addition, the Cognitive Neurology Unit has over 13,000 patient visits per year.

Exclusion criteria include a history of seizures prior to the onset of AD, current use of an antiepileptic medication, current use of a medication known to lower seizure threshold (e.g. bupropion or a neuroleptic), presence of parkinsonism, significant cerebrovascular disease, other CNS disease or major depression. Subjects will be screened for depression with the Geriatric Depression Scale and excluded if they score greater than 9⁴⁷. Participants receiving standard treatments for dementia including cholinesterase inhibitors, memantine and serotonergic selective reuptake inhibitors may participate.

4. Crossover Design, Randomization, and Blinding

This is a within-subject, crossover study. Each subject will receive one of 3 study drug regimens at each session:

- Placebo
- Low dose levetiracetam (2.5 mg/kg)

c. High dose levetiracetam (7.5mg/kg)

A computer-generated, blocked randomization list will be generated that will randomly assign subjects to one of 6 groups. The order of drug administration will be counterbalanced to avoid pitfalls of the crossover repeated measures design.

- Group 1: A, B, C
- Group 2: A, C, B
- Group 3: B, A, C
- Group 4: B, C, A
- Group 5: C, A, B
- Group 6: C, B, A

The BIDMC research pharmacy will provide for randomization and blinding. Patients and investigators will be blinded to study group.

5. Study Procedures

Details and timing of the study procedures are listed below in the section "Study Plan".

- a. Demographics and baseline characteristics
- b. Medical history
- c. Neurologic history, including date of onset and progression of AD, history of prior seizures, and history of other neurological disorders.
- d. Recent and concomitant medications
- e. Assessment of renal function (blood urea nitrogen and creatinine)
- f. Vital signs
- g. At screening and at each visit: Systolic and diastolic blood pressure, heart rate, and respiratory rate; weight

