Participants will undergo declarative memory testing with the Free and Cued Selective Reminding Test, a task that is particularly sensitive to hippocampal function ⁴⁸. In addition, a short battery will be administered to test executive function, naming, visuospatial ability and semantic function (Trail Making Test Parts A+B, Phonemic fluency Test, Boston Naming Test 15-item version, clock drawing, category fluency). The primary endpoint for memory testing will be the free recall score from the Free and Cued Selective Reminding Test. This battery is fairly brief (30 min) but sensitive to both hippocampal function and changes in other cognitive realms impaired in AD.

p. Adverse events observed by investigator or reported spontaneously by the subject

6. Study Plan

The following assessments and procedures will be done at each study visit:

a. Screening visit

1. Informed consent
2. Demographics and baseline characteristics
3. Medical history
4. Neurologic history
5. Recent and concomitant medications
6. Blood collection for blood urea nitrogen and creatinine)
7. Vital signs: Systolic and diastolic blood pressure, heart rate, and respiratory rate; weight
8. Physical exam
9. Neurological exam
10. Mini-Mental Status Examination

b. Visits #1-3 (identical procedures, visit length 5-7 hours)

1. Vital signs: Systolic and diastolic blood pressure, heart rate, and respiratory rate; weight
2. Physical exam
3. Neurological exam
4. IV catheter placement
5. EEG (60 minute recording)
6. Study drug infusion (20 minutes)
7. Vital signs at 10, 20, 30 minutes after infusion
8. Imaging paradigm (60 minutes)
9. Behavioral testing (60-90 minutes)
10. Adverse events

There will be scheduled breaks between tests and scheduled lunch

c. Telephone follow-up

1. Follow up for adverse effects

B. Statistical Considerations

Sample Size Justification:

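### The Aim 2 correlations of change scores carry no visit adjustment; counterbalancing protects treatment means but does not stop visit trends in both measures from inducing a correlation

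*Combined protocol and SAP*

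**What the plan says.** Section B1 states Aim 2 as two correlations. Hypothesis 1 is "Decreases in hippocampal perfusion will correlate with improvements in" declarative and spatial memory scores. Hypothesis 2 links falls in hippocampal perfusion to rises in cortical perfusion. The analysis is in section B3.B, Data Analysis, Imaging Data: "Lastly, we will test for correlations between behavioral measures of memory and regional changes in CBF in hippocampus and whole brain". The expected sign is given there too: "We predict that decreases in hippocampal perfusion will paradoxically correlate with improved declarative memory performance". The same paragraph predicts that hippocampal falls will go with rises in association cortex. Neither correlation is given a visit, period or sequence term.

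On timing, section B1 says: "After drug administration, repeat EEG, ASL-MRI perfusion imaging, and behavioral testing will be conducted". The visit list in B3.A.6 repeats the same procedures at all three visits. EEG is recorded before dosing as well as after; perfusion and memory are not.

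On order effects, section B3.A.4 will "randomly assign subjects to one of 6 groups", one for each order of the three treatments, and adds: "The order of drug administration will be counterbalanced to avoid pitfalls of the crossover repeated measures design". In the perfusion analysis, "we will use a repeated measures ANOVA with hippocampal perfusion and session (placebo, 2.5mg/kg and 7.5mg/kg) being the factors", so session there means treatment and not visit number. The phrase about accounting for repeated measures belongs to the whole-brain drug-versus-placebo model, not to these correlations.

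**The concern.** Without a same-day baseline, a change in perfusion or memory needs a second visit, normally the placebo visit. For half the orders the drug visit comes after placebo, and for the other half before it. In a group mean a visit trend then cancels. In a correlation across subjects it does not, because the lag differs between subjects and is the same number in both of a subject's change scores.

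Suppose free recall rises with practice (the plan mentions no alternate test forms) while the ratio of hippocampal to visual-cortex perfusion falls. Subjects who had placebo first then show better memory and lower perfusion on drug; subjects who had drug first show the reverse. That is the negative correlation Hypothesis 1 predicts, produced by order alone. If both measures drift the same way, the induced correlation is positive and could hide a true association. These correlations are the only stated tests of the two Aim 2 hypotheses.

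**Working it through.** **The plan's own figure.** The only power statement is 72%, for the fall in hippocampal perfusion (B3.B). The table in B2 gives 0.96 (SD 0.29) in AD and 0.77 (SD 0.17) in controls. The difference is 0.19 and the root mean square SD is √((0.29² + 0.17²)/2) = 0.2377. For two independent groups of 20 and an assumed two-sided 5% z test, power is Φ(0.19/(0.2377·√(2/20)) − 1.96) = Φ(0.57) = 71.5%. The figure reproduces, but it concerns Aim 1. No figure is given for the correlations.

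**Inputs.** From the documents: 20 randomized subjects, three treatments, six orders. Assumed: high dose minus placebo as the contrast, a two-sided 5% Pearson test, independent errors in the two measures, no drug effect and no true association. Trends are in within-subject SDs per visit.

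**Lag.** Over the six orders, high-dose visit minus placebo visit is +2, +1, +1, −1, −1, −2. The mean is 0 and the variance is (4+1+1+1+1+4)/6 = 2. Low dose minus placebo has the same distribution. For the mean of both doses minus placebo the lags are ±1.5 or 0, with variance 1.5.

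**Induced correlation, linear trends.** With unit within-subject SD a difference of two visits has error variance 2. For trends g (memory) and h (perfusion), the covariance of the change scores is 2gh and their variances are 2+2g² and 2+2h², so

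r = gh / √((1+g²)(1+h²)).

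False positive rates come from 20,000 simulated trials of 20 subjects (three full blocks of six plus two).

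| Memory trend | Perfusion trend | r by formula | False positive rate |
|---|---|---|---|
| 0 | 0 | 0 | 5% |
| +0.5 | 0 | 0 | 5% |
| +0.5 | −0.25 | −0.125/√(1.25·1.0625) = −0.11 | 7% |
| +0.5 | −0.5 | −0.25/1.25 = −0.20 | 14% |
| +1 | −0.5 | −0.5/√(2·1.25) = −0.32 | 29% |
| +1 | −1 | −1/2 = −0.50 | 71% |

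With trends of +0.5 in both measures the sign flips: r is about +0.20, and about 0.2% of trials are significant in the predicted direction.

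**Single step after the first visit.** The difference in step is +1 in the two orders with placebo first, −1 in the two with high dose first, and 0 in the other two, a variance of 2/3. Then r = gh/√((3+g²)(3+h²)). Opposite steps of 0.5 SD give −0.25/3.25 = −0.08 and about 6% false positives; +1 and −0.5 give about 9%; opposite steps of 1 SD give −1/4 = −0.25 and about 19%.

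**After adjustment.** With two visit terms, leaving 20 − 2 − 2 = 16 degrees of freedom, the rate returns to about 5% for either shape. Adjusting for linear lag alone also gives about 5% under linear trends, but it is incomplete under a step. The covariance of step and lag is (2+1+2+1)/6 = 1, so lag explains 1²/(2 · 2/3) = 75% of the step's variance. With steps of 2 SD in both measures, lag adjustment still rejects in about 20% of trials; two visit terms give about 5%.

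**The case against.** Four arguments carry weight.

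- **Both measures must drift, and in opposite directions, for the bias to favour the prediction.** This stands. A practice gain in memory alone leaves the test at 5%.
- **Hippocampal perfusion is expressed relative to visual cortex.** A proportional global fall, for instance from getting used to the scanner, cancels in that ratio. This stands: what matters is a drift of the hippocampus relative to visual cortex, and the documents give no evidence for or against one.
- **The largest rates need large trends.** If the test-retest correlation were 0.75 (assumed), the within-subject SD of perfusion would be 0.29·√0.25 = 0.145. A trend of 1 SD per visit would then add up to 0.29 over two intervals, more than the whole AD-control difference of 0.19. The 71% case is an upper end, not an expectation.
- **This is a pilot, and the correlations are in neither the primary nor the secondary outcome list.** That limits the weight of the point. It does not remove it, since no other test of the Aim 2 hypotheses is stated.

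The plan also leaves the unit of analysis and the dose contrast of the correlation open. Change scores across subjects follow naturally from Aim 2; high dose minus placebo is a choice made here for the calculation.

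A reader might infer that habituation common to all regions would falsely support Hypothesis 2. It would not: drift in the same direction induces a positive correlation, against the prediction. False support needs hippocampal and cortical perfusion to drift in opposite directions.

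**Conclusion.** The point holds as a conditional weakness of the Aim 2 correlations. The design removes visit trends from mean treatment contrasts when the orders are balanced, but it leaves a lag variance of 2 shared by both change scores, and the plan adjusts for none of it. How far this distorts the test depends on trends that the documents do not give: negligible if only one measure drifts, modest for small or first-visit-only drifts, and serious only if both drift strongly. The direction can favour the prediction or work against it.

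Two stronger readings are not supported. One is that a significant Aim 2 correlation would have to be an order artefact; nothing in the documents shows that either measure drifts. The other is that the repeated measures ANOVAs are biased by order; their treatment comparisons rest on means, which counterbalancing does protect, and they are not at issue here.

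**What to change.** In section B3.B, Imaging Data, specify both Aim 2 correlations as partial correlations of the drug-minus-placebo differences, adjusted for visit with two visit terms. For each subject, the visit 2 term is +1 if the drug session was visit 2, −1 if the placebo session was, and 0 otherwise; the visit 3 term is built in the same way. In the voxelwise analyses the same two terms enter as covariates. The sentence should name the dose contrast, since the terms depend on it. Linear lag should not be used in place of the two terms, because it leaves part of a first-visit effect in the data.

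The cost is one sentence and two degrees of freedom (18 to 16). Visit number is already recorded, so no new data are needed.
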